***Visit 1 (day -7):***

Qualifying patients will be scheduled for first this visit within 2 weeks of screening visit. Their insulin pump will be downloaded or log of MDI/carbohydrate intake will be collected and appropriate insulin adjustments will be made by the investigator to target fasting blood glucose concentrations between 70-180 mg/dl if possible at all times without having additional hypoglycemia (less than 70 mg/dl). Urine collection container will be provided with instruction to collect urine starting 24 hours before coming for their next visit.

***Visit 2 (day 0):***

Qualifying subjects will be asked to come for the visit in a fasting state (10-12hr fasting). They will be fasting for the entire visit. 24hr urine will be collected, vitals and fingerstick blood glucose and ketones ( $\beta$ -hydroxybutyrate) using the Precision Extra glucose and ketones meter (Abbott Laboratories) and urine Ketostix (Bayer) will be measured. For MDI patients, baseline blood, spot urine, and adipose tissue will be collected. The remainder of this visits' procedures apply only to pump patients. If, ketones measure positive in blood or in urine ( $\geq 0.4$  mM in blood or  $>+1$  in urine) or fasting blood glucose  $<70$  or  $>250$  mg/dl, the acute testing will not take place and patient will be rescheduled. An IV port will be placed in order to obtain blood samples throughout the duration of the visit. Insulin infusion will be stopped, and baseline blood, spot urine, and adipose tissue will be collected. These samples will constitute the baseline for all study measurements. One of the treatment arms will be administered to the patient depending on their cohort (placebo OR exenatide  $5\mu\text{g}$  subcutaneous (same site will be used in 2nd acute study at end of study) injection OR dapagliflozin 10mg (two 5mg) oral tablets OR combination of exenatide  $5\mu\text{g}$  AND

dapagliflozin 10mg (two 5mg) with appropriate placebos in a randomized fashion). Subjects will be fasting throughout the first 6 hr of the visit. Blood (10ml) will be collected every 30 min and spot urine every 1hr for up to 8 hours. Additional blood samples (20ml) will be collected at 1, 2, 4 and 6 and 8 hours for *MNC* isolation. A second adipose tissue biopsy will be collected at 360 min after starting the treatment. Basal insulin Infusion will be restarted at the end of the 360min sample collections, food will be provided, patient will be instructed to deliver a bolus insulin dose through bolus wizard calculator of the insulin pump after entering the grams of carbohydrates and blood glucose (Bolus wizard matches the bolus insulin dose based on individual patient's insulin to carbohydrate ratio and correction factor for high blood glucose). Patients will be monitored for at least 2hr before discharging from center (8hr time point). The subject's blood glucose and ketones ( $\beta$ -hydroxybutyrate) levels will be monitored every 30 minutes and ketones will be also measured in urine using Ketostix every hour to ensure safety. If the BG concentrations exceed 400 mg/dl or blood  $\beta$ -hydroxybutyrate exceeds 2.5mmol/l (or +3 (80mg/dl) or greater in urine) anytime during the 360 minutes following single dose/doses with or without clinical signs and symptoms of DKA like nausea and vomiting then STAT lab sample for CMP will be collected along with research blood sample. Spot urine and adipose tissue biopsy will be collected only if deemed feasible by the investigator present based on the clinical condition of the participant. Basal insulin will be restarted; bolus insulin as per the bolus wizard calculator will be administered and a meal provided. Patient will be discharged only after all laboratory parameters return to pretesting levels with no clinical symptoms of DKA.

This will now mark the end of the acute testing phase and the beginning of the 12 weeks treatment phase. If the HbA1c is  $\geq 7.5\%$ ; then no reduction will be made in dose of insulin while if the HbA1c ranges from 7-7.5% then the basal and pre-prandial insulin doses will be reduced by 5%. All patients will be instructed on how to give the single subcutaneous injection of Exenatide extended release (2mg weekly) or Exenatide extended release placebo (for those in cohort 1), or open label drugs (for those in cohort 2), which will be administered at home the next day. Patients will also be provided with 12 oral tablets of either 5mg placebo or 5mg dapagliflozin (depending on their group assignment and cohort) and instructed to consume 1 tablet in the morning on each of the first 4 days and 2 tablets (10 mg) on days 5, 6 and 7 (and for the rest of the 12 weeks thereafter) and to return to the center on day 7. Urine collection container will be provided and patients instructed to collect 24hr urine before their next visit. The patients will be trained to recognize the symptoms of DKA and to self-test ketones daily and if they develop any symptoms consistent with DKA, including nausea, vomiting, fatigue, confusion, or shortness of breath. Information sheet about above information will be provided to participants. Patients will be instructed to measure ketone bodies in urine samples daily with Ketostix (Bayer) and record it in diary provided. If ketone bodies in urine measure +2 or greater ( $>4\text{mM}$  in urine), patients are required to notify the research center. The investigators will collect all necessary information and advise the patient of any steps to mitigate the risk of DKA or to visit the closest emergency department and to inform emergency staff of their participation in a research study.

;

**Visit 3 (Week 1):** Vitals will be measured and fasting blood and 24hr urine samples will be collected. Carbohydrate intake/insulin injection logs, food diaries, or CGM/pump data will be reviewed and documented. Patients will be provided with 3 weeks supply of Exenatide extended release or Exenatide extended release placebo and 10mg dapagliflozin or placebo tablets depending on their cohort. Urine collection container will be provided and patients instructed to collect 24hr urine before their next visit. Insulin doses will be titrated to target blood glucose between 70-180 mg/dl if possible at all times without having additional hypoglycemia (less than 70 mg/dl). Ketostix will be dispensed and patients will be instructed to measure ketone bodies in a spot urine sample daily and reported as described in visit 2.

**Visit 4 (Week 4):** Patient physical and vitals will be measured, fasting blood and 24hr urine samples will be collected. Carbohydrate intake/insulin injection logs, food diaries, or CGM/pump data will be reviewed and documented. Patients will be provided with 4 weeks supply of Exenatide extended release or Exenatide extended release placebo and 10mg dapagliflozin or placebo tablets depending on their cohort. Urine collection container will be provided and patients instructed to collect 24hr urine before their next visit. Insulin doses will be titrated to target blood glucose between 70-180 mg/dl if possible at all times without having additional hypoglycemia (less than 70 mg/dl). Ketostix will be dispensed and patients instructed to measure ketone bodies in a spot urine sample daily and reported as described in visit 3.

**Visit 5 (Week 8):** Vitals will be measured and fasting blood and 24hr urine samples will be collected. Carbohydrate intake/insulin injection logs, food diaries, or CGM/pump data will be reviewed and documented. Patients will be provided with 4 weeks supply of Exenatide extended release or Exenatide extended release placebo and 10mg dapagliflozin or placebo tablets depending on their cohort. Urine collection container will be provided and patients instructed to collect 24hr urine before their next visit. Insulin doses will be titrated to target blood glucose between 70-180 mg/dl if possible at all times without having additional hypoglycemia (less than 70 mg/dl). Ketostix will be dispensed and patients instructed to measure ketone bodies in a spot urine sample daily and reported as described in visit 3.

**Visit 6 (Week 12):** Subjects will be asked to come for the visit in a fasting state (10-12hr fasting). The will be fasting for the entire visit. Once the patient arrives to the research center, a complete physical examination will be done, 24hr urine will be collected, vitals and fingerstick blood glucose and ketones ( $\beta$ -hydroxybutyrate) using the Precision Extra glucose and ketones meter (Abbott Laboratories) will be measured. For MDI patients, baseline blood, spot urine, and adipose tissue will be collected. The remainder of this visits' procedures apply only to pump patients. An IV port will be placed in order to obtain blood samples throughout the duration of the visit. Insulin infusion will be stopped. Baseline blood, spot urine, and adipose tissue will be collected immediately after stopping insulin. One of the treatment arms will be administered to the patient according to their original group assignment as in Visit 2. All samples and monitoring procedures will be done as in Visit 2. Insulin doses will be titrated to target blood glucose between 70-180 mg/dl if

possible at all times without having additional hypoglycemia (less than 70 mg/dl) before discharge from study.

Phone calls will be made by our team at weeks 2, 6 and 10 to ensure safety. Patients will also be instructed to call if they develop unexpected symptoms.

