Safety data (vitals, CBC, CMP, urinary markers) will be collected at screening, during and at end of the study. STAT CMP will be done when glucose or ketones exceeds 400mg/dl and 2.5mM, respectively or any signs of DKA is observed during the acute testing phase. If, ketones measure positive in blood or in urine ( $\geq 0.4$  mM in blood or  $>+1$  in urine) or fasting blood glucose  $<70$  or  $>250$  mg/dl, the acute testing will not take place and patient will be rescheduled. Injection site reactions, mycotic infections and complications of IV and biopsy collection will also be monitored, volume control and hypoglycemia will be monitored and collected at every visit. Physical examination will be performed at 2, 4, 8 and 12 weeks visits and safety assessments performed. Ketone bodies will measured daily by patient in urine. LDL-C levels will be monitored at screening visit, 4 and 12 weeks. Pregnancy will be tested at screening, 4 and 12 weeks. Insulin dose titration will done at every visit to avoid hypoglycemia. Phone calls will be made for safety and compliance follow-up at least 3 time during the study. The patients, however, will be instructed to

report any adverse event or safety related information via phone as soon as it occurs. All safety data will be reviewed by the PI or sub-investigators within 1-2 days of collection.

If the BG concentrations exceed 400 mg/dl or blood  $\beta$ -hydroxybutyrate exceeds 2.5mmol/l (or +3 (80mg/dl) or greater in urine) anytime during the 360 minutes following single dose/doses with no clinical signs and symptoms of DKA like nausea and vomiting then blood sample, spot urine and adipose tissue biopsy will be collected immediately, basal insulin will be restarted; bolus insulin as per the bolus wizard calculator will be administered and a meal provided. Patients will be instructed to come back at the 24-hour mark.

Patients will be instructed to measure ketone bodies in urine samples daily with Ketostix (Bayer) and record it in diary provided. If ketone bodies in urine measure +2 or greater (>4mM in urine), patients are required to notify the research center.

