## **25.0 Compensation for Participation**

*25.1 Describe the amount and timing of any compensation to subjects, including monetary, course credit, or gift card compensation.*

Response:

*Visit 1 Insulin adjustment \$25,*

*Visit 2 Single dose \$175, Including 2 fat BX, (\$50 per bx) and 6 blood draws.\**

*Visit 3 Blood Draw \$50.00,*

*Visit 4 Blood draw \$50.00,*

*Visit 5 Blood work \$50.00,*

*Visit 6 Single dose \$175, Including 2 fat BX, (\$50 per bx) and 6 blood draws.\**

*Total compensation for all completed visits: \$525.00\**

*\*Those patients that are not on inulin pumps and do not partake in the acute testing will only be compensated for a baseline blood draw and one fat biopsy at Visit 2 and 6 for a total of \$100 per visit. Total compensation for these patients that complete all visits will be \$375.*

All study participants will receive a check in the mail for their time and effort.

**N/A:** This study is not enrolling subjects, or is limited to records review procedures only. This section does not apply.

**N/A:** There is no compensation for participation. This section does not apply.

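### The day-0 ketone limit is written only for the pump-only acute test, so no explicit rule holds baseline sampling or drug start in an injection (MDI) patient who is ketone-positive

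*Combined protocol and SAP*

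**What the plan says.** Section 6.1 admits both pump patients and patients on four or more injections a day. In Section 10.1, Visit 2, the fasting glucose and ketone readings are listed before the two groups are separated. The injection group's baseline is then taken without a condition: "For MDI patients, baseline blood, spot urine, and adipose tissue will be collected". The next sentence limits the rest of the visit to pump patients, and the limit follows it: "The remainder of this visits' procedures apply only to pump patients. If, ketones measure positive in blood or in urine". The triggers are blood ketones of 0.4 mM or more, urine above +1, or fasting glucose below 70 or above 250 mg/dl.

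Section 21.2 repeats the triggers without the pump-only sentence. The stated consequence is the same in both places: "the acute testing will not take place and patient will be rescheduled". Section 25.1 confirms that some patients are "not on inulin pumps and do not partake in the acute testing".

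The Visit 2 text then opens the 12-week phase for all patients. The weekly injection is one "which will be administered at home the next day". The tablets are taken as "1 tablet in the morning on each of the first 4 days and 2 tablets (10 mg) on days 5, 6 and 7". No ketone condition is attached to either. Insulin is cut by 5% at this point if HbA1c is 7 to 7.5%. Section 17.1 uses the week-0 fasting value as baseline for the primary endpoint.

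**The concern.** The protocol treats ketoacidosis as the central hazard of adding dapagliflozin in type 1 diabetes, and it takes a ketone reading the day before treatment starts. For a pump patient, a positive reading postpones the acute test. Because the 12-week phase follows that test, it in effect also postpones baseline and drug start. For an MDI patient the same reading has no stated consequence. The patient can give the baseline sample and begin a ketogenic drug on schedule.

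What is at stake is mainly safety in a small number of patients. A lesser matter is that the baseline rule for the primary endpoint differs between pump and MDI patients.

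**Working it through.** The plan gives no figure on this point, so the main check is to set every rule on ketones or glucose side by side and ask whether it acts on an MDI patient's pre-dose day-0 ketone reading.

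| Rule | Where | Whom and when | Holds MDI baseline or drug start on day-0 ketones? |
|---|---|---|---|
| Ketone and glucose limit | 10.1, Visit 2 | After the pump-only sentence; cancels acute test | No |
| Same limit repeated | 21.2 | No pump-only sentence; action is still on the acute test | Not stated |
| Rescue at glucose >400 mg/dl or ketones >2.5 mmol/l | 10.1, Visit 2 | Within 360 minutes of the acute dose | No |
| Insulin review and titration | 10.2 schedule; 21.2 | Every patient at Visit 2; concerns glucose and insulin | No |
| Home Ketostix, call at +2 | 10.1, Visit 2 | Daily, after dispensing; urine only | No |
| Stay on 5 mg if significant ketonuria at 5 mg | 21.1 | After drug start | No |
| Insulin floor of 0.5 units/kg | 21.1 | Insulin dose | No |
| Safety data review | 21.2 | Within 1-2 days; can end after the first dose | No |
| Removal at the investigator's discretion | 20.2 | Any time; not tied to this reading | No |
| Eligibility | 6.1, 6.2 | No ketone or ketoacidosis-history criterion | No |

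Timing for an MDI patient: the 24-hour return is described only within the acute study, so the next planned clinic reading is Visit 3 (day 7 in the Visit 2 text, day 8 in the schedule). Four days at 5 mg and the step to 10 mg on day 5 come before it. The first planned call is at week 2.

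**How many patients (illustration).** The documents give neither the MDI share nor the spread of fasting ketones in this population.

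- Section 3.1 preliminary data, n = 10, with ± read as standard error: beta-hydroxybutyrate mean 0.11 mM, SD = 0.02 × √10 = 0.063 mM.
- Share at or above 0.4 mM: 0.36% if lognormal, 0.0002% if normal.
- Dapagliflozin recipients: 30 in cohort 1, plus 20 × 2/3 in cohort 2 (equal thirds assumed) = 43.3.
- MDI share assumed 20 to 50%: 8.7 to 21.7 patients.
- At 0.36%: 0.03 to 0.08 patients. At an assumed upper end of 5%: 0.43 to 1.08 patients.

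**Primary endpoint (illustration).** In the same preliminary data, total ketones rise from 0.11 + 0.32 = 0.43 mM to 0.39 + 0.53 = 0.92 mM. The rise is 0.49 mM, and 0.49/0.43 = +114%. Assume the same rise from a higher baseline:

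- Beta-hydroxybutyrate 0.4 mM: total 0.72 mM; 0.49/0.72 = +68%, which is 46 points lower.
- Beta-hydroxybutyrate 0.8 mM: total 1.12 mM; 0.49/1.12 = +44%, which is 70 points lower.

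Completers per arm after 15% drop-out: 20 × 0.85 = 17 (Section 17.2) or 15 × 0.85 ≈ 13 (cohort 1 alone). One such patient lowers an arm mean by 46/17 = 2.7 to 70/17 = 4.1 points with 17 completers, or 46/13 = 3.5 to 70/13 = 5.4 points with 13. The planned difference is 50 points. The meter reads only beta-hydroxybutyrate; acetoacetate is 0.32/0.43 = 74% of baseline total ketones, so the limit would cap the baseline only in part.

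**The case against.** The strongest reply is that the pump-only sentence is loosely placed. Read strictly, it would also remove drug dispensing and ketone training from MDI patients, which is plainly not meant, since the treatment phase is addressed to all patients. Section 21.2 carries no such restriction and says the patient is rescheduled, so a generous reader could extend it to MDI patients. That stands as an ambiguity. It does not supply a hold: the action named in Section 21.2 is still on the acute test, and neither baseline sampling nor drug start is mentioned.

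Second, the limit protects a period of up to six hours without insulin plus a 10 mg dose. MDI patients keep their insulin and start at 5 mg. This is a fair reason for a different ketone threshold, but the plan gives none. It is also a good reason not to extend the glucose limits to them.

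Third, the other safeguards are real. A reader might infer that nothing at all is done about day-0 readings in MDI patients. The documents do not support that. Glucose is acted on through insulin review and titration at Visit 2 (Sections 10.2 and 21.2) and review of glucose-monitor traces at each visit (Section 19.2). The home test and the 5 mg cap partly cover the dose step, and the investigator may remove a patient at risk. Visit 3 falling after the step is deliberate and applies to pump patients too, as does the 5% insulin cut. The next-day wording attaches to the injection; the start day of the tablets is inferred.

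Fourth, a reader might take the preliminary ketoacidosis case, which came within 48 hours of the step to 10 mg, as evidence for this gap. It is weak support. The patient was on insulin, liraglutide and dapagliflozin, with insulin down to 0.39 units/kg, below the floor now imposed, and the case is not attributed to ketosis before drug start.

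**Conclusion.** The point holds as a modest safety gap. As written, no explicit rule holds baseline sampling or drug start in an MDI patient with a positive ketone reading on day 0, and the existing safeguards cover the consequences only in part. The table rests on the text alone. The delay of baseline and drug start in pump patients is inferred from the order of procedures.

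The frequency of 0.03 to 1.1 patients rests on an assumed MDI share, an assumed upper rate of 5%, and ten preliminary patients who were on liraglutide, whereas this trial excludes recent GLP-1 receptor agonist use. It shows only that the number is probably small.

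A reader might infer that the primary comparison is biased. It is not: the missing rule applies alike to all randomized arms. Nor is a large distortion shown. Holding the final value at 0.92 mM would give (0.92 − 0.72)/0.72 = +28% for a baseline of 0.72 mM, but that assumes the patient's higher ketone level leaves no trace on drug. With the same rise added, one patient moves an arm mean by roughly 3 to 5 points against a planned 50. The case for a change is the safety one.

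**What to change.** In Section 10.1, Visit 2, move the ketone limit ahead of the pump-only sentence. State in both Visit 2 and Section 21.2, for all patients: *if blood beta-hydroxybutyrate is 0.4 mM or more, or urine ketones are above +1, baseline sampling and the start of study drug are rescheduled, as is the acute test in pump patients.* Restrict the pump-only sentence to the acute insulin-withdrawal test, and keep the <70 and >250 mg/dl glucose limits there. If the investigators judge that another ketone threshold suits MDI patients, who continue insulin, they should state it, with the reason and the action.

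The cost is one or two sentences, using readings already taken, and an occasional rescheduled Visit 2 for an MDI patient.

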- Prior history of a malignant disease requiring chemotherapy or patients with a prior history of bladder cancer regardless of treatment
- Alcoholism or drug addiction.
- Hypertriglyceridemia (>400 mg/dl).
- Any other life-threatening, non-cardiac disease
- Uncontrolled hypertension (BP > 160/95 mm of Hg)
- Patients with hypotension or at risk for volume depletion due to co-existing conditions or concomitant medications, such as loop diuretics or recently donated >500ml of blood should have careful monitoring of their volume status
- Pregnant or breastfeeding patients or patient not willing to use two barrier method contraception during study period (unless sterilized or have an IUD)
- Use of hormonal medications, anti-obesity drugs or weight loss medications (prescription or OTC) and medications known to exacerbate glucose tolerance (such as isotretinoin, GnRH agonists, glucocorticoids, anabolic steroids, C-19 progestins) stopped for at least 8 weeks. Use of anti-androgens that act peripherally to reduce hirsutism such as 5-alpha reductase inhibitors (finasteride, spironolactone, flutamide) stopped for at least 4 weeks
- Presence of hypersensitivity to dapagliflozin or other SGLT2 inhibitors (e.g. anaphylaxis, angioedema, exfoliative skin conditions)
- Known hypersensitivity or contraindications to use GLP1 receptor agonists (exenatide, liraglutide)
- Known hypersensitivity to heparin/ IV catheter equipment.
- Eating disorders (anorexia, bulimia) or gastrointestinal disorders
- Having a history of bariatric surgery

- Debilitating psychiatric disorder such as psychosis or neurological condition that might confound outcome variables
- Use of an investigational agent or therapeutic regimen within 30 days of study
- Participation in any other concurrent clinical trial

6.3 Indicate specifically whether you will include any of the following special populations in your study using the checkboxes below.

**NOTE: Members of special populations may not be targeted for enrollment in your study unless you indicate this in your inclusion criteria.**

Response: NA

- Adults unable to consent
- Individuals who are not yet adults (infants, children, teenagers)
- Pregnant women
- Prisoners

6.4 Indicate whether you will include non-English speaking individuals in your study. **Provide justification if you will exclude non-English speaking individuals.**

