## 8.0 Eligibility Screening

8.1 Describe **screening procedures** for determining subjects' eligibility. Screening refers to determining if prospective participants meet inclusion and exclusion criteria.

 Include all relevant screening documents with your submission (e.g. screening protocol, script, questionnaire).

Response:

Prospective participants will be asked to read and understand the consent and any questions they may have regarding the protocol will be answered. If the subject wants to participate in the study, they will be asked to sign the informed consent form. The subject's medical history and current medications will be obtained as well as their blood pressure and vitals. A physical examination will also be done. Blood samples will be taken in order to evaluate HbA1c, CBC, CMP and liver and kidney functions and pregnancy status. The patient's insulin pump will be uploaded for pump patients, and food/insulin logs will be collected for MDI patients. Patients meeting all the inclusion and exclusion criteria based on all screening tests will be enrolled in the study.

N/A: There is no screening as part of this protocol.

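### No pregnancy test is scheduled between screening and first dose, a gap of up to 21 days (longer if day 0 is rescheduled)

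*Combined protocol and SAP*

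**What the plan says.** Section 6.2 excludes "Pregnant or breastfeeding patients or patient not willing to use two barrier method contraception during study period (unless sterilized or have an IUD"). Section 21.4 adds that the consent form carries a birth-control commitment and that a participant who becomes pregnant leaves the study at once.

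At screening (section 8.1), consent comes first: "they will be asked to sign the informed consent form". Then "Blood samples will be taken in order to evaluate HbA1c, CBC, CMP and liver and kidney functions and pregnancy status". For Visit 1, labelled day -7, section 10.1 says: "Qualifying patients will be scheduled for first this visit within 2 weeks of screening visit".

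On arrival at Visit 2 (day 0), "24hr urine will be collected, vitals and fingerstick blood glucose and ketones" are taken, and the list closes with "ketones meter (Abbott Laboratories) and urine Ketostix (Bayer) will be measured". For pump patients, positive ketones or a fasting glucose outside the stated range lead to a new date: "the acute testing will not take place and patient will be rescheduled. An IV port will be placed". If the checks pass, "Insulin infusion will be stopped, and baseline blood, spot urine, and adipose tissue will be collected", and the single dose follows. Basal insulin resumes after the 360-minute samples. Drug for the 12-week phase is supplied at this visit, and the first weekly injection is taken at home the following day.

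The schedule table in section 10.2 marks a pregnancy test at screening and at Visits 4, 5 and 6 (weeks 4, 8 and 12). Section 21.2 lists screening and weeks 4 and 12.

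**The concern.** The plan intends that no pregnant patient is exposed, and section 21.4 treats fetal risk as not applicable on that basis. That position holds only if pregnancy status is known when exposure begins, and no test is scheduled near that moment. A pregnancy missed at screening, or begun after it, would not be looked for before a pump patient's insulin is withheld for up to 6 hours, or before any patient receives study drug. The plan acknowledges diabetic ketoacidosis as a risk of this treatment (section 21.1), so the first insulin-withdrawal test is a natural point for the check. The table does place a pregnancy test on the day of the second acute test (Visit 6), which repeats the Visit 2 procedures, but not on the day of the first.

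**Working it through.** **Is the table read correctly?** The pregnancy row has seven visit columns (screening and Visits 1 to 6). Four are marked: screening, 4, 5 and 6. Visits 1, 2 and 3 are blank. Other rows of the same table agree with the visit text: physical examination at Visits 4 and 6, and adipose biopsy at Visits 2 and 6. The blank cells are therefore not a column shift. Section 21.2 differs from the table on week 8 but also has no day-0 test.

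**Is there a test elsewhere?** The Visit 2 arrival checks are the 24-hour urine, vitals, fingerstick glucose and ketones, and urine Ketostix. The postponement rule uses ketones and glucose only. Section 19.2 names pregnancy testing among the safety assessments, and section 19.5 says safety data are collected at every visit. Neither assigns a pregnancy test to Visit 2.

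**Age of the last test at first dose.** Inputs are the visit windows in section 10.1.

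- Screening to Visit 1: at most 14 days.
- Visit 1 (day -7) to Visit 2 (day 0): 7 days.
- Pump patients, dosed on day 0: 14 + 7 = 21 days, plus any rescheduling delay. No limit is stated.
- Patients on multiple daily injections (MDI), with no acute dose and a start on day 1: 21 + 1 = 22 days.

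**Interval between consecutive scheduled tests.** Table days are 28, 56 and 84 for weeks 4, 8 and 12.

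| Interval | As planned | With a day-0 test |
|---|---|---|
| Screening to day 0 | no day-0 test | up to 21 days |
| Screening to week 4 | up to 21 + 28 = 49 days | split at day 0 |
| Day 0 to week 4 | no day-0 test | 28 days |
| Week 4 to week 8 | 56 - 28 = 28 days | 28 days |
| Week 8 to week 12 | 84 - 56 = 28 days | 28 days |

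The longest interval, which spans first dose, falls from 49 to 28 days. The age of the last test at first dose falls from up to 21 days to 0 for pump patients, and from up to 22 days to about 1 for MDI patients.

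**The case against.** The case for leaving the plan alone has several parts. There is a blood test at screening, an exclusion for those unwilling to use contraception, a signed commitment made before the screening bloods, a withdrawal rule, and testing at weeks 4, 8 and 12. Visit 1 is a face-to-face contact before dosing, section 26.4 has patients questioned at each visit, and section 20.1 withdraws anyone who develops an excluded condition. HbA1c, CBC and CMP are likewise not repeated at Visits 1 or 2, so pregnancy was handled like the other eligibility bloods. The documents quantify no fetal harm from one dose or from the insulin interruption, which is monitored every 30 minutes with rescue thresholds. A day-0 test would itself miss a very recent conception.

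Much of this stands as mitigation. The residual risk is contraceptive failure or a pregnancy too early to detect at screening, and no figure can be put on it. But none of these safeguards is a test before first dose. The comparison with the other bloods is also weak: the plan marks pregnancy four times, against two for HbA1c and CBC and three for CMP, so it already treats pregnancy as something to recheck despite the contraception commitment. Visit 3 and the week-2 call come after exposure has begun.

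Two points of detail are fair. Rescheduling affects only pump patients who fail the glucose or ketone check, and its length cannot be estimated. Section 10.1 also does not say which urine the arrival Ketostix uses.

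**Conclusion.** The concern holds. Screening is the only pregnancy test before first dose. It can be 21 days old for pump patients, with no upper limit after rescheduling, and 22 days old for MDI patients. The figures use the longest permitted window and assume that day -7 is kept and that MDI patients start on day 1. They are schedule intervals, not probabilities of harm. The number of women of child-bearing potential is not given, so no expected count can be derived. This is a patient-safety point with slight effect on the analysis. It is worth correcting because the remedy is cheap and enforces the plan's own exclusion.

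**What to change.** Add to Visit 2 in section 10.1, placed before the sentence that limits the rest of the visit to pump patients:

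> On arrival, women of child-bearing potential will have a urine pregnancy test, using the urine taken for the Ketostix check or a fresh arrival sample, not the baseline spot urine. A negative result is required before insulin is stopped (pump patients) and before any study drug is given or dispensed (all patients). The test is repeated if the visit is rescheduled.

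Mark Visit 2 in the pregnancy row of the section 10.2 table. As an editorial alignment, change section 21.2 to list screening, day 0 and weeks 4, 8 and 12, since it now omits the week-8 test that the table contains.

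The cost is one test strip per woman of child-bearing potential, at a visit where urine is already strip-tested, plus short edits in three sections. The downside is an occasional screen failure discovered on day 0.
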